9.2.3.1 Screening/Baseline (Visit 1)

The following procedures will be performed at the baseline visit. Data will be collected from the medical charts and recorded on the CRF when they are available.

- Collect signed informed consent form. A copy of the signed consent should be given to the patient.
- Assess the eligibility according to the inclusion/exclusion criteria and record the date of inclusion
- Randomize the eligible patients into one of the study groups (standard of care OR standard of care with advanced educational intervention)
- Collect demographic data (date of birth, gender, race, education level, height, weight, and alcoholic status [defined as ≥ 8 units of consumption per week])
- Record AF-related medical histories
- Record the following comorbidities:
 - Currently ongoing diseases: Hypertension, diabetes, congestive heart failure, left ventricular dysfunction, abnormal kidney function (chronic dialysis, renal

NIS Protocol Page 21 of 46

transplantation, serum creatinine $\geq 200~\mu mol/L$, or eGFR < 60 mL/min/1.73 m²), abnormal liver function (chronic hepatic disease [e.g., cirrhosis] or biochemical evidence of significant hepatic derangement [e.g., bilirubin > 2 × upper limit of normal, in association with AST/ALT/ALP > 3 × upper limit normal]), major bleeding, and predisposition to bleeding/anemia.

- Prior events: Vascular disease (myocardial infarction, peripheral artery disease, and complex aortic plaque), ischemic heart disease, stroke, transient ischemic attack, and thromboembolism
- Collect the latest results of serum creatinine (will be used to calculate CrCl by Cockcroft-Gault formula) and eGFR prior to the baseline
- To acquire HAS-BLED score:
 - Record the latest results of bilirubin, AST, ALT, ALP, INR, and PT prior to the baseline
 - Record if the subject is receiving chronic dialysis or had undergone renal transplant due to abnormal renal function prior to the baseline; and medication usage predisposing to bleeding (antiplatelet agents or NSAIDs) within 1 month prior to the baseline
- The educator delivers advanced education to subjects in the experimental group.
- Record the use of dabigatran (dose, date of administration)
- Record the concomitant therapies for AF or stroke prevention within 1 month prior to the baseline (generic name or name of the therapy)
- Record the occurrence of stroke and thromboembolic events, if any
- Record the occurrence of bleeding-related events, if any
- Do safety reporting if any dabigatran relevant ADR, fatal AEs, and pregnancies occurs

Information to be collected from screen failure individuals

The screening log entry with demographic information and the primary reason for not continuing or ineligibility must be completed for all screened patients that do not qualify for study entry. No CRF other than the screening log will be collected from these patients. The subject number of ineligible patients should be kept. The following enrolments will be numbered in sequence.

9.2.3.2 Month 3 ± 6 weeks (Visit 2)

The following procedures will be performed at 3 months after the baseline. Data will be collected from the medical charts and recorded on the CRF when they are available.

- Record the weight and alcoholic status (defined as ≥ 8 units of consumption per week)
- Record the active or newly onset of comorbidities since the baseline (during baseline to Month 3). Comorbidities include hypertension, diabetes, congestive heart failure, vascular disease (myocardial infarction, peripheral artery disease, and complex aortic plaque),

NIS Protocol Page 22 of 46

ischemic heart disease, left ventricular dysfunction, stroke, transient ischemic attack, thromboembolism, abnormal kidney function (chronic dialysis, renal transplantation, serum creatinine $\geq 200~\mu mol/L$, or eGFR $<60~mL/min/1.73~m^2$), abnormal liver function (chronic hepatic disease [e.g., cirrhosis] or biochemical evidence of significant hepatic derangement [e.g., bilirubin $>2~\times$ upper limit of normal, in association with AST/ALT/ALP $>3~\times$ upper limit normal]), major bleeding, and predisposition to bleeding/anemia.

- Collect the results of serum creatinine (will be used to calculate CrCl by Cockcroft-Gault formula) and eGFR if available in medical record. Only the values within the allowed window and closest to 3 months will be collected.
- To acquire HAS-BLED score:
 - Record the results of bilirubin, AST, ALT, ALP, INR, and PT if available in medical record. Only the values within the allowed window and closest to 3 months will be collected.
 - Record if the subject is receiving chronic dialysis or have undergone renal transplant due to abnormal renal function, and medication usage predisposing to bleeding (antiplatelet agents or NSAIDs) during baseline to 3 months
- The educator delivers advanced education to subjects in the experimental group.
- Record the use of dabigatran (dose, date of administration)
- Record the change of concomitant therapies for AF or stroke prevention after baseline (generic name or name of the therapy)
- Complete the measurement of MMAS-8 score
- Record the occurrence of stroke and thromboembolic events, if any
- Record the occurrence of bleeding-related events, if any
- Do safety reporting if any dabigatran relevant ADR, fatal AEs, and pregnancies occurs

9.2.3.3 Month 6 ± 6 weeks (Visit 3)

The following procedures will be performed at 6 months after the baseline. Data will be collected from the medical charts and recorded on the CRF when they are available.

- Record the weight and alcoholic status (defined as ≥ 8 units of consumption per week)
- Record the active or newly onset of comorbidities since Visit 2 (during Month 3 to Month 6). Comorbidities include hypertension, diabetes, congestive heart failure, vascular disease (myocardial infarction, peripheral artery disease, and complex aortic plaque), ischemic heart disease, left ventricular dysfunction, stroke, transient ischemic attack, thromboembolism, abnormal kidney function (chronic dialysis, renal transplantation, serum creatinine ≥ 200 μmol/L, or eGFR < 60 mL/min/1.73 m²), abnormal liver function (chronic hepatic disease [e.g., cirrhosis] or biochemical evidence of significant hepatic derangement [e.g., bilirubin > 2 × upper limit of normal, in association with AST/ALT/ALP > 3 × upper limit normal]), major bleeding, and predisposition to bleeding/anemia.

NIS Protocol Page 23 of 46

• Collect the results of serum creatinine (will be used to calculate CrCl by Cockcroft-Gault formula) and eGFR if available in medical record. Only the values within the allowed window and closest to 6 months will be collected.

- To acquire HAS-BLED score:
 - Record the results of bilirubin, AST, ALT, ALP, INR, and PT if available in medical record. Only the values within the allowed window and closest to 6 months will be collected.
 - Record if the subject is receiving chronic dialysis or have undergone renal transplant due to abnormal renal function, and medication usage predisposing to bleeding (antiplatelet agents or NSAIDs) during 3 to 6 months
- The educator delivers advanced education to subjects in the experimental group.
- Record the use of dabigatran (dose, date of administration)
- Record the change of concomitant therapies for AF or stroke prevention since the last visit (generic name or name of the therapy)
- Complete the measurement of MMAS-8 score
- Record the occurrence of stroke and thromboembolic events, if any
- Record the occurrence of bleeding-related events, if any
- Do safety reporting if any dabigatran relevant ADR, fatal AEs, and pregnancies occurs

9.2.3.4 Month 9 ± 6 weeks (Visit 4)

The following procedures will be performed at 9 months after the baseline. Data will be collected from the medical charts and recorded on the CRF when they are available.

- Record the weight and alcoholic status (defined as ≥ 8 units of consumption per week)
- Record the active or newly onset of comorbidities since Visit 3 (during Month 6 to Month 9). Comorbidities include hypertension, diabetes, congestive heart failure, vascular disease (myocardial infarction, peripheral artery disease, and complex aortic plaque), ischemic heart disease, left ventricular dysfunction, stroke, transient ischemic attack, thromboembolism, abnormal kidney function (chronic dialysis, renal transplantation, serum creatinine ≥ 200 μmol/L, or eGFR < 60 mL/min/1.73 m²), abnormal liver function (chronic hepatic disease [e.g., cirrhosis] or biochemical evidence of significant hepatic derangement [e.g., bilirubin > 2 × upper limit of normal, in association with AST/ALT/ALP > 3 × upper limit normal]), major bleeding, and predisposition to bleeding/anemia.
- Collect the results of serum creatinine (will be used to calculate CrCl by Cockcroft-Gault formula) and eGFR if available in medical record. Only the values within the allowed window and closest to 9 months will be collected.
- To acquire HAS-BLED score:

NIS Protocol Page 24 of 46

- Record the results of bilirubin, AST, ALT, ALP, INR, and PT if available in medical record. Only the values within the allowed window and closest to 9 months will be collected.
- Record if the subject is receiving chronic dialysis or have undergone renal transplant due to abnormal renal function, and medication usage predisposing to bleeding (antiplatelet agents or NSAIDs) during 6 to 9 months
- The educator delivers advanced education to subjects in the experimental group.
- Record the use of dabigatran (dose, date of administration)
- Record the change of concomitant therapies for AF or stroke prevention since the last visit (generic name or name of the therapy)
- Complete the measurement of MMAS-8 score
- Record the occurrence of stroke and thromboembolic events, if any
- Record the occurrence of bleeding-related events, if any
- Do safety reporting if any dabigatran relevant ADR, fatal AEs, and pregnancies occurs

9.2.3.5 Month 12 ± 6 weeks (Visit 5)

The following procedures will be performed at 12 months after the baseline. Data will be collected from the medical charts and recorded on the CRF when they are available.

- Record the weight and alcoholic status (defined as ≥ 8 units of consumption per week)
- Record the active or newly onset of comorbidities since the visit 4 (during Month 9 to Month 12). Comorbidities include hypertension, diabetes, congestive heart failure, vascular disease (myocardial infarction, peripheral artery disease, and complex aortic plaque), ischemic heart disease, left ventricular dysfunction, stroke, transient ischemic attack, thromboembolism, abnormal kidney function (chronic dialysis, renal transplantation, serum creatinine ≥ 200 μmol/L, or eGFR < 60 mL/min/1.73 m²), abnormal liver function (chronic hepatic disease [e.g., cirrhosis] or biochemical evidence of significant hepatic derangement [e.g., bilirubin > 2 × upper limit of normal, in association with AST/ALT/ALP > 3 × upper limit normal]), major bleeding, and predisposition to bleeding/anemia.
- Collect the results of serum creatinine (will be used to calculate CrCl by Cockcroft-Gault formula) and eGFR if available in medical record. Only the values within the allowed window and closest to 12 months will be collected.
- To acquire HAS-BLED score:
 - Record the results of bilirubin, AST, ALT, ALP, INR and PT if available in medical record. Only the values within the allowed window and closest to 12 months will be collected.
 - Record if the subject is receiving chronic dialysis or have undergone renal transplant due to abnormal renal function, and medication usage predisposing to bleeding (antiplatelet agents or NSAIDs) during 9 to 12 months

NIS Protocol Page 25 of 46

- Record the use of dabigatran (dose, date of administration)
- Record the change of concomitant therapies for AF or stroke prevention since the last visit (generic name or name of the therapy)
- Complete the measurement of MMAS-8 score
- Record the occurrence of stroke and thromboembolic events, if any
- Record the occurrence of bleeding-related events, if any
- Do safety reporting if any dabigatran relevant ADR, fatal AEs, and pregnancies occurs

9.2.4 Study discontinuation

Boehringer Ingelheim reserves the right to discontinue the study overall or at a particular study site at any time for the following reasons:

- (1) Failure to meet expected enrolment goals overall or at a particular study site
- (2) Emergence of any efficacy/safety information that could significantly affect the continuation of the study, or any other administrative reasons.
- (3) Violation of Good Clinical Practice (GCP), Good Epidemiological Practice (GEP), or Good Pharmacoepidemiology Practice (GPP) (as applicable), the study protocol, or the contract by a study site or investigator, disturbing the appropriate conduct of the study

The investigator/the study site will be reimbursed for reasonable expenses incurred in case of study termination (except in case of the third reason).

9.3 VARIABLES

9.3.1 Exposures

Being an NIS, the prescription of dabigatran will be in accordance with the Summary of Product characteristics and physician's discretion. Treatment record of dabigatran will be collected and recorded on CRF across the 12 months of study period. Data to be collected include start/end date of administration, dose, and the reason for dose adjustment or interruption.

9.3.2 Outcomes

9.3.2.1 Primary outcomes

The proportion of patients with high adherence to dabigatran treatment which is defined as achieving the MMAS-8 score of 8 points at 12 months in patients with and without advanced educational intervention

NIS Protocol Page 26 of 46

9.3.2.2 Secondary outcomes

- (1) The proportion of patients with high adherence to dabigatran treatment which is defined as achieving the MMAS-8 score of 8 points at 3, 6, and 9 months in patients with and without advanced educational intervention
- (2) The proportion of patients with medium (MMAS-8 score: 6-7 points) and low (MMAS-8 score < 6 points) adherence to dabigatran treatment at 3, 6, 9, and 12 months in patients with and without advanced educational intervention
- (3) The mean MMAS-8 score at 3, 6, 9, and 12 months in patients with and without advanced educational intervention
- (4) The discontinuation rate of dabigatran and reasons for discontinuation (switch or stop treating dabigatran) in patients with and without advanced educational intervention

9.3.2.4 Morisky 8-Item Medication Adherence Questionnaire (MMAS-8)

The MMAS-8 is an 8-item structured, self-report measure that assesses medication adherence. It has been proved to be a valuable resource to address adherence concerns, such as forgetting to take medications or discontinuing medications without guidance. If a patient scores higher on the scale, they are evaluated as more adherent. If they score lower on the scale, they are presumed to be struggling with non-adherence.

The validated Chinese MMAS-8 will be used to evaluate the adherence to dabigatran at baseline and every follow-up visit. Patients are considered to have low adherence with scores less than 6, medium adherence with scores of 6 to 7, and high adherence with a score of 8.

NIS Protocol Page 27 of 46

9.3.2.5 Stroke and thromboembolic events

Stroke and thromboembolic events to be captured include but not limited to stroke, myocardial infarction, peripheral arterial occlusion, pulmonary embolism, venous thrombosis, transient ischemic attack, and thromboembolism.

Investigators and study staffs should check if patients experience above events across the 12 months of follow-up. Whenever a stroke and thromboembolic event happens, the investigator should judge its severity (mild, moderate, or severe) and record the event on the CRF.

9.3.2.6 Bleeding-related events

Bleeding-related events to be captured include but not limited to intracranial, gastrointestinal, intraspinal, intraocular, pericardial, intra-articular, intramuscular, perioperative, retroperitoneal, and genitourinary bleeding.

Bleeding-related events will be further classified into "Major bleeding" or "Minor bleeding" based on the following definitions:

- Major bleeding: Bleeding that is fatal, symptomatic in critical area or organ (intracranial, life-threatening, or requiring surgery), causing hemoglobin (Hb) fall of ≥ 2.0 g/L or leading to transfusion of ≥ 2 units.
- Minor bleeding: Bleeding not meeting the criteria for major bleeding but requiring medical intervention, change in antithrombotic therapy, or considered clinical relevant by the physician.

Investigators and study staffs should check if patients experience above events across the 12 months of follow-up. Whenever a bleeding-related event happens, the investigator should judge its severity (mild, moderate, or severe) and record the event on the CRF.

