9.4 DATA SOURCES

As this is an NIS, no diagnostic or monitoring procedures additional to the standard of care and routine practice (except for the additional education delivered to the experimental group) will be applied to the patients. All the assessment will be performed by the investigator if they are deemed necessary for the medical treatment procedure.

This study will collect the data from medical charts and MMAS-8 questionnaires. Investigators or delegated site staffs will record the data on the CRF. Data source includes questionnaires, hospital discharge files, abstracts of primary clinical records, electronic medical records, clinical databases, administrative records such as eligibility files, prescription drug files, biological measurements, exposure/work history record reviews, etc.

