9.7.1 Main analysis

The analyses will be mainly descriptive to gain an understanding of the characteristics of the sample studied.

Continuous variables will be reported as number, mean, standard deviation (SD), minimum, maximum, and 95% confidence interval (CI). Categorical variables will be summarized as number and frequency or percentage with observed (non-missing) data.

Analysis of endpoints:

- The primary outcome is to describe the proportion of patients with high adherence to dabigatran treatment which is defined as achieving MMAS-8 score of 8 points at 12 months for each group. Subjects without MMAS-8 value recorded at 12 months will be excluded from the analysis of primary endpoint.
- The Mean MMAS scores at 3, 6, 9 and 12 months will be compared between patients with and without advanced educational intervention using Chi-square, Fisher's exact, or other appropriate tests for categorical data and using t-test or Wilcoxon rank-sum test for continuous data. Similarly, subjects without MMAS-8 value recorded at a specific visit will be excluded from the analysis of corresponding secondary endpoints.
- Other secondary outcomes in patients with and without advanced educational intervention separately and further outcomes only within pooled patient set (e.g., comorbidities, stroke/thromboembolic/bleeding events, risk factors, ADR, etc.) will all be analyzed in a descriptive manner
- All tests will be done under a statistical level of 0.05.

NIS Protocol Page 33 of 46

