9.8 QUALITY CONTROL

Before the study launch, participating physicians will be trained on the protocol, safety reporting (Section 11) and study conduct procedures by Boehringer Ingelheim (or designee).

In keeping with the non-interventional design employed in this study, site interaction (e.g., direct contact between site study staff or patients and representatives of the call center or the study coordinating center) is minimized.

Source data verification will be performed for critical study outcomes in this study. At any time during the course of the study, the site study staff may contact designated personnel for clarification of the study conduct. All information will be kept confidential.

During the study, the occurrence of any protocol violations will be determined. After these actions have been completed and the clinical database has been declared to be complete and accurate, it will be locked.

To ensure the data accuracy, completeness, and reliability, quality control will be the ongoing, concurrent review of data collection forms for completion and logic. The research staffs will preserve documented data from all sources on the CRF, including lab test results, chart records, treatment conditions, physical examination, concomitant medication, and any safety information.

Boehringer Ingelheim or designated CRO will assure database quality processes are followed including the review of the data entered into the CRFs by investigational staffs for completeness and accuracy, and in accordance with the DVP.

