9.10.2.1 Source documents

Source documents are original documents, data, and records from which the subject's CRF data are obtained. These documents include but not limited to hospital records, clinical and office charts, laboratory and pharmacy records, diaries, microfiches, radiographs, MMAS-8

NIS Protocol Page 35 of 46

questionnaires, and correspondence. CRF records may be considered as source data if the CRF is the original recording (i.e., there is no any other written or electronic record of data).

Source documents provide evidence for the existence of the patient and substantiate the integrity of the data collected. Source documents are filed at the investigator's site in a locked cabinet.

Data reported on the CRFs that are transcribed from source documents must be consistent with the source documents or the discrepancies must be explained. The investigator may need to request previous medical records or transfer records; also, current medical records must be available.

For paper CRFs, the following data need to be derived from source documents:

- Patient identification (gender, date of birth, etc.)
- Patient participation in the study (substance, study number, patient number, the date when the patient consents the participation)
- Dates of patient's visits, including prescription of dabigatran and date of assessment
- Medical history or clinical diagnosis (including concomitant diseases and concomitant therapies)
- ADRs related to dabigatran and outcome events (i.e., stroke, thromboembolic events, bleeding-related events)
- Originals or copies of laboratory results or examinations
- Conclusion of patient's participation in the study
- Other study-specific variables

The physician must keep the original informed consent form signed by the patient (a signed copy must be given to the patient).

The investigator should maintain a list of appropriately qualified persons to whom he/she has delegated trial duties. All persons authorized to make entries and/or corrections on CRFs will be included on the authority form.

No information in source documents about the identity of the patients will be disclosed. No study document can be destroyed without prior written agreement between Boehringer Ingelheim and the investigator. Should the investigator wish to assign the study records to another party or move them to another location, he/she must notify Boehringer Ingelheim in advance.

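### Major bleeding can be met by a haemoglobin fall of only 2.0 g/L (0.2 g/dL), which is hard to tell from re-test variation; the unit needs checking

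*Protocol*

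**What the plan says.** Protocol section 9.3.2.6 splits bleeding events into two classes. The major class opens with "Major bleeding: Bleeding that is fatal, symptomatic in critical area or organ (intracranial, life-threatening, or requiring surgery") and continues with "causing hemoglobin (Hb) fall of ≥ 2.0 g/L or leading to transfusion of ≥ 2 units". Minor bleeding is the remainder: "Bleeding not meeting the criteria for major bleeding but requiring medical intervention, change in antithrombotic therapy, or considered clinical relevant by the physician".

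The same section asks for a separate grade for every bleed: "Whenever a bleeding-related event happens, the investigator should judge its severity (mild, moderate, or severe) and record the event on the CRF".

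The haemoglobin threshold appears only here. The readable SAP text has no definition of major bleeding. Haemoglobin is not among the laboratory data in the collection schedule (Protocol Table 1, note 6). Section 9.4 says that patients undergo "no diagnostic or monitoring procedures additional to the standard of care and routine practice", apart from the education itself, so any haemoglobin value comes from routine care.

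Describing bleeding events is a secondary objective (Protocol section 8). Section 9.7.1 says that "further outcomes only within pooled patient set (e.g., comorbidities, stroke/thromboembolic/bleeding events, risk factors, ADR, etc.) will all be analyzed in a descriptive manner".

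**The concern.** The other routes to major bleeding are death, symptomatic bleeding in a critical site and transfusion of at least 2 units. A fall of 2.0 g/L does not belong with these, and g/L in place of g/dL is an easy slip to make.

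Read literally, the rule also inverts the two classes. A bleed that needs no intervention but is followed by a haemoglobin 0.2 g/dL lower, attributed to the bleed, is major. A bleed that needs medical intervention and a change of antithrombotic therapy, without that fall, is minor.

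What is at stake is the meaning of the reported major/minor split. Some bleeds with paired haemoglobin values could be counted as major on a difference that laboratory and day-to-day variation produce unaided. Major bleeding also appears in the comorbidity list and in the bleeding item of HAS-BLED. An effect there is possible but has not been shown.

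**Working it through.** The threshold is a definition, so there is no figure in the plan to reproduce. The check has four parts.

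**1. Unit.** 1 L = 10 dL, so 2.0 g/L ÷ 10 = 0.2 g/dL. As a share of an assumed haemoglobin: 2/120 = 1.67%, 2/140 = 1.43%, 2/160 = 1.25%.

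**2. Is it sufficient alone?** Yes, given a bleed. The criteria form one list of alternatives joined by 'or', and no further condition is attached to the fall beyond the bleed having caused it.

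**3. Can such a fall be told from re-test variation?** The documents give neither a haemoglobin level nor its variability, so both are assumptions: haemoglobin 120 to 160 g/L, and total CV (within-person plus assay) 0.5% to 4%. With no true change, the difference of two values has SD √2 × CV × Hb, so

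P(apparent fall ≥ 2.0 g/L) = Φ(−2 / (√2 × CV × Hb)).

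| CV | Hb 120 g/L | Hb 140 g/L | Hb 160 g/L |
|---|---|---|---|
| 0.5% | 0.009 | 0.022 | 0.039 |
| 1% | 0.119 | 0.156 | 0.188 |
| 2% | 0.278 | 0.307 | 0.329 |
| 3% | 0.347 | 0.368 | 0.384 |
| 4% | 0.384 | 0.400 | 0.413 |

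Example: at 140 g/L and CV 2%, the SD of the difference is √2 × 0.02 × 140 = 3.96 g/L, and Φ(−2/3.96) = 0.307.

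The same calculation with an assumed within-person SD s in g/dL, Φ(−0.2/(s√2)), gives 0.240, 0.319, 0.362 and 0.389 for s = 0.2, 0.3, 0.4 and 0.5.

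The 95% limit for a difference, 1.96 × √2 × CV × Hb, runs from 3.3 g/L (CV 1%, Hb 120) to 17.7 g/L (CV 4%, Hb 160). It exceeds 2.0 g/L throughout CV 1% to 4%.

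**4. How precise would haemoglobin have to be?** Setting 2.0 g/L equal to the 95% limit at 140 g/L:

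- two-sided: CV = 2 / (1.96 × √2 × 140) = 0.52%
- one-sided: CV = 2 / (1.645 × √2 × 140) = 0.61%

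Over 160 to 120 g/L, taking both limits together, this is 0.45% to 0.72%. Only a total CV below roughly these values would let a fall of 2.0 g/L stand out.

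For scale only, and not as a proposed threshold: the same number read in g/dL would be 20 g/L, ten times larger. An apparent fall of that size with no true change has probability at most 1.4% (Hb 160, CV 4%) on the CV 1% to 4% grid.

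**The case against.** **The slip is inferred.** The threshold appears once and nothing readable contradicts it. If g/L was intended, the affected bleeds are classified as the protocol directs. A fault in reading the PDF cannot be ruled out, and SAP pages 18 and 19, directly after the secondary outcomes, have no readable text in this copy. This stands. It is why the first request is to check the unit, and why the slip is called likely and not proven. The inversion between the classes would still need explaining if g/L were intended.

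**The percentages are not misclassification rates.** They describe pairs with no true change, whereas the rule covers patients who have bled and whose fall the investigator attributes to the bleed. This also stands: no rate among bleeds can be derived. But a fall of this size within re-test variation gives the investigator little basis for attribution.

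**The consequence is small.** Bleeding is pooled and descriptive, every bleed is captured and graded for severity whatever its class, and few may have paired haemoglobin values. All true, and it limits the severity. It does not make the major-bleeding count interpretable.

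**Source checks may mitigate it.** Section 9.8 says "Source data verification will be performed for critical study outcomes in this study", and section 9.10.2.1 requires source support for "ADRs related to dabigatran and outcome events (i.e., stroke, thromboembolic events, bleeding-related events"). Verification confirms that the record matches the chart. A fall of 0.2 g/dL, correctly transcribed, passes and still counts as major.

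**A re-review would look only for downgrades.** That follows from the logic: a larger threshold can only remove events that qualified on haemoglobin alone.

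**Conclusion.** The concern holds. As written, a fall of 0.2 g/dL attributed to a bleed makes that bleed major with no other criterion met. No readable text corrects this.

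The conversion, the 'or' structure and the inversion between classes come from the Protocol alone. The difficulty of separating such a fall from re-test variation rests on assumed variability: 2% to 40% of unchanged pairs at 140 g/L over CV 0.5% to 4%, and 0.9% to 41% when haemoglobin also varies from 120 to 160 g/L. The number of bleeds affected cannot be known from the documents.

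The readable text contains no between-arm test of bleeding. The point should be fixed before bleeding results are reported, but it does not threaten the study's main question.

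**What to change.** 1. Check the unit of the haemoglobin criterion against the bleeding definition the sponsor adopted, the CRF and the full SAP. If the unit is wrong, correct Protocol section 9.3.2.6. If g/L was intended, say so and explain how it fits with the other major criteria.
2. If the text changes, notify sites.
3. Then re-review from source documents every event classed as major on haemoglobin alone, starting with those graded mild. The readable text does not show whether the CRF records which criterion was met, so these events may have to be identified from the charts.
4. If the event form does not already ask for them, add the haemoglobin values before and after the bleed where the chart has them. No extra blood tests are needed.

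The cost is a one-line correction, a site note, two optional chart fields and the re-review. If the threshold proves larger than printed, the major-bleeding count can only stay the same or fall.
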